4.1.4.1 Dose escalation of afatinib for MTD determination

The MTD will be determined as the highest dose at which no more than 1/6 patients experienced DLT. The MTD will be determined when the last patient included into the dose finding part completed his/her 1st treatment cycle and is evaluable for DLTs.

The dose finding part will use a rolling six design ([R12-4744](#)). The dose escalation and de-escalation and the MTD determination will be performed as described in [Table 4.1.4.1:1](#)

Table 4.1.4.1:1 Dose escalation and de-escalation schedule and determination of MTD

No. of enrolled patients per dose cohort	DLT data among the enrolled patients			Enrolling dose level for the next patient	
	No. with DLT	No. without DLT	No. with DLT data pending	MTD not exceeded	MTD exceeded **
2	0 or 1	Any	Any	d	--
	2	0	0	d - 1	--
3	0	3	0	d + 1	d
	1	Any	Any	d	--
	>=2	Any	Any	d - 1	--
4	0	4	0	d + 1	d
	0	Other	Other	d	d
	1	Any	Any	d	d
	>=2	Any	Any	d - 1	d - 1
5	0	5	0	d + 1	d
	0	Other	Other	d	d
	1	Any	Any	d	d
	>=2	Any	Any	d - 1	d - 1
6	0	5, 6	1, 0	d + 1	MTD
	0	Other	Other	Suspend***	Suspend
	1	5	0	d + 1	MTD
	1	Other	Other	Suspend	Suspend
	>=2	Any	Any	d - 1	d - 1

Table adapted from Skolnik et al JCO 2008 Table 1 pp 191 ([R12-4744](#).)

Note this table does not take into account unevaluable patients.

* d is the current dose level; d + 1 and d - 1 represent dose escalation and de-escalation, respectively.

Proprietary confidential information.

© 2017 Boehringer Ingelheim International GmbH or one or more of its affiliated companies. All rights reserved.

This document may not - in full or in part - be passed on, reproduced, published or otherwise used without prior written permission.

** MTD exceeded means that the 'd + 1' dose level has ≥ 2 out of 3 to 6 patients with DLT (which is why there is no escalation in any of the listed scenarios).

*** 'Suspend' means there is not enough information to determine the next patient's dose level, one needs to wait until pending DLT data become available.

Note that the Rolling 6 design allows enrolling up to 6 patients on each dose cohort. The first cohort of patients will start with dose level 0 (i.e. 80% of adult dose) as listed in [Table 4.1.3:1](#). As soon as at least two patients are treated at dose level 0, the dose level for the third and subsequent patients will be determined based on the number of patients determined to have experienced DLT, those determined without DLT, and those with DLT data pending for the first treatment course, as illustrated in the first row of [Table 4.1.4.1:1](#). For illustration purpose, an example (considering 4 patients treated on dose level 0) is given below:

- 1) If DLT data of all 4 patients are available and none of them observed with DLT, the dose level may be escalated and the 5th patient will be enrolled to dose level 1
- 2) If data is not yet available for one or more of the first 4 patients, or if one patient with DLT is observed, then the 5th patient will remain on dose level 0; the decision on further dose escalation or de-escalation will be made based on the rules illustrated for a 5-patient cohort
- 3) If more than 2 patients are observed with DLTs, the dose will be de-escalated and the 5th patient will be enrolled to dose level -1

If scenario 1) occurs, dose level 1 becomes dose 'd' in [Table 4.1.4.1:1](#). The process repeats after two patients are enrolled on dose level 1.

If scenario 3) occurs, dose level 0 exceeds the MTD, and dose level -1 is the lowest dose level allowed in this trial. Up to six patients will then be treated on this level, if $\leq 1/6$ patients with DLT, then dose level -1 will be the MTD; if ≥ 2 patients with DLT, then there will be no MTD.

Similarly, suppose the trial has been escalated to higher dose levels, e.g. dose level 3, and ≥ 2 patients had DLT, and if dose level 2 treated less than 6 patients previously, then the dose will be de-escalated to level 2 to fill up to 6 patients and the decision will be made according to the last column in [Table 4.1.4.1:1](#).

As shown in [Table 4.1.4.1:1](#), in order for a dose level to be the MTD, there must have been 6 patients treated on the dose level (at most one patient can have DLT) and the next higher dose level exceeded MTD (≥ 2 patients with DLT). The exception to this rule is if none of the 4 dose levels exceeds MTD, then dose level 3 will be MTD.

If a patient experiences DLT (for definition refer to [Table 4.1.4.1:2](#)), therapy may be continued at a reduced dose (for dose reduction, refer to [Table 4.1.4.3:1](#)) after recovery of the respective adverse event(s) to pre-dose CTCAE grade(s). The investigator shall liaise with BI and ask for confirmation of the dose of the trial drug before a new treatment course is started for any patient. In questionable cases, the DMC might be involved in decision making. If a patient is not eligible for further therapy, the patient has to discontinue further treatment with the trial drug.

Proprietary confidential information.

© 2017 Boehringer Ingelheim International GmbH or one or more of its affiliated companies. All rights reserved.

This document may not - in full or in part - be passed on, reproduced, published or otherwise used without prior written permission.

Table 4.1.4.1:2 Dose limiting toxicities

Dose limiting toxicity (DLT)

DLTs are defined as any of the following events that are considered related to afatinib:

1. CTCAE grade 4 hematologic toxicity lasting for 7 days
 2. CTCAE Grade 3 or 4 non-hematologic toxicity (except fever grade 3).
 3. CTCAE Grade 2 or higher decrease in cardiac left ventricular function
 4. CTCAE Grade 2 or higher worsening of renal function as measured by serum creatinine, newly developed proteinuria, or newly developed decrease in glomerular filtration rate
 5. CTCAE Grade 2 diarrhoea persisting for 7 or more days, despite supportive treatment (loperamide treatment or other effective anti-diarrhoeal medication)
 6. CTCAE Grade 2 nausea and/or vomiting persisting for 7 or more days despite antiemetic treatment
 7. CTCAE grade 5 events
-

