4.1.4.3 Dose reduction of afatinib

Treatment related toxicities will be managed by treatment interruptions and subsequent dose reductions of afatinib according to the schedule described in [Table 4.1.4.3: 1](#). Dose reductions will apply to individual patients only. Once the treatment dose has been reduced, it cannot be increased later.

To prevent the development of more severe adverse events, treatment related diarrhoea, nausea and vomiting or rash should be managed early and proactively as described in [Section 4.2](#).

Proprietary confidential information.

© 2017 Boehringer Ingelheim International GmbH or one or more of its affiliated companies. All rights reserved.

This document may not - in full or in part - be passed on, reproduced, published or otherwise used without prior written permission.

Table 4.1.4.3:1 Dose reduction scheme for afatinib

AE type and CTCAE Grade	Action	Dose reduction scheme

Events related to study drug:
 
 • Diarrhoea Grade 2 persisting for 7 or more consecutive days despite adequate anti-diarrhoeal medication/hydration • Reduced renal function to \geq Grade 2 as measured by serum creatinine, proteinuria or decrease in glomerular filtration rate of more than 50% from baseline • Any drug related AE Grade \geq3 	
Pause treatment until patient has recovered to Grade \leq1 or baseline¹.
 
Resume treatment at reduced dose according to schedule opposite.
 
If patient has not recovered to Grade \leq1 or baseline¹ within 14 days, study treatment must be permanently discontinued².
	
If patient was treated at dose level 3, resume treatment at dose level 2
 
If patient was treated at dose level 2, resume treatment at dose level 1
 
If patient was treated at dose level 1, resume treatment at dose level 0
 
If patient was treated at dose level 0, resume treatment at dose level -1
 
If patient was treated at dose level -1, discontinue afatinib.

Acute onset and/or unexplained worsening of pulmonary symptoms (dyspnoea requiring supplementation of oxygen with cough and/or fever)
	
Pause afatinib while clinical assessment to exclude ILD is completed.
	
If ILD is ruled out as a cause of symptoms, grade symptoms and relatedness and report as AEs. If AEs are not related, resume afatinib at current dose.
 
If ILD is confirmed, discontinue afatinib.

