
Acute onset of symptoms indicative of keratitis
	
Pause afatinib while clinical assessment of keratitis is ongoing.
	
If a diagnosis of ulcerative keratitis is confirmed, treatment with afatinib should be discontinued. Unless the treatment benefit for the patient outweighs the risks of worsening keratitis (blindness) in the opinion of the investigator.

Acute onset of symptoms indicative of cardiac failure and/or CTCAE Grade \geq 2 LVEF decrease and/or \geq20% decrease of LVEF from baseline
	
Pause afatinib while clinical assessment is ongoing and until patient recovers to Grade \leq1 or baseline¹
	
If patient has not recovered despite appropriate treatment to Grade \leq1 or baseline¹ within 14 days, study treatment must be permanently discontinued²

1 Baseline is defined as the CTCAE Grade at the start of treatment

2 In the event that the patient is deriving obvious clinical benefit according to the investigator's judgement, further treatment with afatinib will be decided in agreement between the sponsor and the investigator.

In the event of any unrelated adverse events, the investigator may choose to interrupt the medication for up to 14 days, but no dose reduction should occur once treatment is resumed.

Proprietary confidential information.

© 2017 Boehringer Ingelheim International GmbH or one or more of its affiliated companies. All rights reserved.

This document may not - in full or in part - be passed on, reproduced, published or otherwise used without prior written permission.

If the medication is interrupted for more than 14 days, the decision to continue with afatinib will be made by the BI clinical monitor in agreement with the investigator.

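### One DLT criterion, persistent related Grade 2 nausea or vomiting, has no trigger in the dose-reduction table, and the DLT text and that table give different restart grades

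*Protocol*

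**What the plan says.** **The event is a DLT.** Criterion 6 of protocol Table 4.1.4.1:2 is "CTCAE Grade 2 nausea and/or vomiting persisting for 7 or more days despite antiemetic treatment", when considered related to afatinib.

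**It falls under Section 4.1.4.3.** Section 5.2.2.1 lists DLT as a protocol-specified adverse event of special interest and requires any related one to be managed under Section 4.1.4.3. That section opens: "Treatment related toxicities will be managed by treatment interruptions and subsequent dose reductions of afatinib according to the schedule described in"; the schedule meant is Table 4.1.4.3:1.

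**The table's triggers.** The first row covers three related events:
- "Diarrhoea Grade 2 persisting for 7 or more consecutive days despite adequate anti-diarrhoeal medication/hydration";
- renal function reduced to Grade 2 or worse, with the GFR limb worded as "decrease in glomerular filtration rate of more than 50% from baseline";
- any related event of Grade 3 or higher.

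Further rows cover acute pulmonary symptoms, keratitis, and cardiac failure or LVEF decrease. For the first row the action is to pause until Grade 1 or lower, or baseline, and resume one level down. If there is no such recovery "within 14 days, study treatment must be permanently discontinued". Footnote 2 relaxes the stop only for obvious clinical benefit.

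**Other text that touches the event.**
- Section 4.1.4.3 refers the reader to Section 4.2 for management: "treatment related diarrhoea, nausea and vomiting or rash should be managed early and proactively as described in".
- Section 4.1.4.1 says that after a DLT therapy may continue at a reduced dose, by reference to the same table, "after recovery of the respective adverse event(s) to pre-dose CTCAE grade(s".
- Below the table, after a sentence on unrelated events, comes "If the medication is interrupted for more than 14 days, the decision to continue with afatinib will be made by the BI clinical monitor"; the investigator has to agree.

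**The concern.** A site managing a child with this DLT is sent to a table that, read literally, neither pauses nor reduces the dose. Criterion 5, the parallel Grade 2 diarrhoea criterion, has an almost identical line in the table, so an oversight is more plausible than a deliberate exclusion. The pointer to Section 4.2 does not fill the gap: the subsections of 4.2.2 deal with diarrhoea, skin reactions and mucositis, and none deals with nausea or vomiting.

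The restart rule is a second, separate problem. Section 4.1.4.1 and the table set different recovery grades for the same patient.

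The matter is still live although dose finding is complete. Section 5.2.1 has DLTs monitored throughout the trial and makes events leading to dose reduction a safety endpoint, which SAP Section 7.8.1 tabulates. SAP Table 6.2:1, code C3, records a pause, reduction or stop after an AE or DLT that departs from the protocol. For this event the standard to judge it against is unclear, and sites may act differently.

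**Working it through.** No sample size, power or error rate is involved. The check sets the DLT criteria against the dose-reduction table, then compares the two restart rules.

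**1. Each DLT criterion (Table 4.1.4.1:2) against Table 4.1.4.3:1**

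| DLT criterion | Line in the dose-reduction table |
|---|---|
| 1. Grade 4 haematologic, 7 days | General line, related Grade 3 or higher |
| 2. Grade 3 or 4 non-haematologic | General line, related Grade 3 or higher |
| 3. Grade 2 or higher LV function decrease | Cardiac row |
| 4. Grade 2 or higher renal worsening | Renal line; GFR limb worded differently |
| 5. Grade 2 diarrhoea, 7 or more days | Diarrhoea line |
| 6. Grade 2 nausea/vomiting, 7 or more days | None |
| 7. Grade 5 | Death; no dose rule needed |

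Survivable criteria: 7 − 1 = 6. Of these, 4 are matched (1, 2, 3, 5), 1 is matched with different wording (4), and 1 has no line (6): 4 + 1 + 1 = 6.

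**2. Restart rule by starting grade**

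Footnote 1 of the table defines baseline as the CTCAE grade at the start of treatment, which is the pre-dose grade.

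| Starting grade | Section 4.1.4.1 requires | Table 4.1.4.3:1 accepts | Agree? |
|---|---|---|---|
| 0 | Grade 0 | Grade 0 or 1 | No |
| 1 | Grade 1 | Grade 1 or lower | Yes |
| 2 or higher | Starting grade | Grade 1 or lower, or starting grade | Yes, both accept the starting grade |

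The conflict arises only for a Grade 0 starter who recovers to Grade 1. Section 4.1.4.1 is the outlier. Grade 1 or lower, with or without the baseline alternative, is also the recovery grade in the table's cardiac row, in Section 4.2.1 for LVEF, in Table 4.2.2.1:1 for diarrhoea (Grade 2 persisting 7 days, and Grades 3 and 4), and in Table 4.2.2.3:1 for Grade 3 and 4 mucositis.

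**3. Size of the dose step that a trigger line would require**

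Section 4.1.3 places the MTD at 80% of the adult dose, which is level 0, so the step is to level -1. From Table 4.1.4:1:
- smallest: 3.5 to 2.5 mL (BSA 0.79 to 0.86 m²), 1.0/3.5 = 28.6%;
- largest: 2.0 to 1.0 mL (BSA below 0.40 m²), 1.0/2.0 = 50.0%;
- tablets at BSA 1.56 m² or more: 30 to 20 mg, 10/30 = 33.3%.

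**4. How many patients**

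The documents give no incidence for criterion 6. As an assumption only, 1% to 10% of up to 38 expansion patients is 38 × 0.01 = 0.38 to 38 × 0.10 = 3.8 patients.

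**The case against.** The strongest reply is that the event is not without rules. Section 5.2.2.1 refers to Section 4.1.4.3 as a whole, and its text calls for interruption and then reduction. Section 4.1.4.1 points any DLT to a reduced dose, and the table's level steps do not depend on the type of event. Section 4.2.2 opens with a rule for any drug-related event: pause if applicable, treat, reduce if applicable. An interruption beyond 14 days goes to the sponsor and investigator. This is partly right, so the claim has to be limited to the missing explicit pause trigger and mandatory 14-day stop. It does not close the gap. The Section 4.1.4.3 text and the Section 4.2.2 rule both refer back to the table, Section 4.1.4.1 only says therapy may continue, and the 14-day sentence follows one about unrelated events, so its scope is arguable.

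A second reply is that the two halves weaken each other. Section 4.1.4.1 is headed as dose escalation for the MTD, and that part is finished. If its rule ends there, the restart conflict is historical. That is fair, but criterion 6 then loses its reduced-dose fallback in the expansion part. If the rule continues, the restart conflict is live. Either reading leaves something to correct.

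Third, waiting for Grade 0 satisfies both restart rules without setting off the table's stop. That is true, but a site following the table would restart at Grade 1 and so depart from Section 4.1.4.1.

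Fourth, C3 cites its tables only as a comment or example, is assessed manually and excludes nobody. That stands, and it limits the statistical consequence.

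Last, other Grade 2 events are left to judgement: persistent rash may lead to a pause, and intolerable mucositis restarts at the same dose. Those events are not DLTs, so the parallel is imperfect.

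**Conclusion.** The concern holds, as a minor point. Criterion 6 is the only one of six survivable DLT criteria without a line in the dose-reduction table. The restart rules conflict for one starting grade, Grade 0.

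The MTD, DLT counts, analysis sets and efficacy endpoints do not change. What changes is the handling of a child with a declared DLT and the consistency of dose-reduction and deviation records in the expansion part. Several safeguards limit the risk: sponsor confirmation of the dose and possible DMC input (Section 4.1.4.1), the investigator's authority to stop treatment (Section 3.3.4.1), and reporting of such events within 24 hours (Section 5.2.2.2).

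The textual findings rest on no numerical assumption. The 0.4 to 3.8 patients rests wholly on the assumed incidence. The mandatory stop would reach fewer still: those unrecovered at 14 days and without obvious clinical benefit.

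**What to change.** 1. Add criterion 6, in its existing wording, to the drug-related triggers in the first row of Table 4.1.4.3:1.
2. In Section 4.1.4.1, replace the pre-dose grade with the table's recovery rule (Grade 1 or lower, or baseline).
3. At the next SAP revision, let deviation C3 cite Table 4.1.4.3:1. It now cites Table 4.1.2.3:1, which the protocol does not contain.

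The cost is one line and one phrase in a protocol amendment and one table number in the SAP, with no new assessments. There is a clinical price. Some patients would take a dose cut of 29% to 50%, and Section 4.1.4.3 does not allow a reduced dose to be raised again. Section 4.1.4.1 already points to that reduction, so the line makes it mandatory rather than new. Patients not recovered within 14 days and without obvious clinical benefit would have to stop.

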4.1.4.2 Intra-patient dose escalation of afatinib

For the patients included in the dose finding part, retreatment and intra-patient dose escalation to the next dose tier may be allowed when this dose tier was considered safe (for dose tiers, refer to [Table 4.1.3:1](#); for dosing, refer to [Table 4.1.4:1](#)). This will allow all patients remaining on treatment to maximize their benefit from treatment, and prevent under-dosing patients in the initial dose cohorts ([Section 3.2](#)).

The decision on when to consider the next higher dose tier safe will be based on a thorough assessment by the steering committee and, if required, by the DMC. Intra-patient dose escalation still needs to be confirmed with the sponsor.

4.1.4.3 Dose reduction of afatinib

Treatment related toxicities will be managed by treatment interruptions and subsequent dose reductions of afatinib according to the schedule described in [Table 4.1.4.3: 1](#). Dose reductions will apply to individual patients only. Once the treatment dose has been reduced, it cannot be increased later.

To prevent the development of more severe adverse events, treatment related diarrhoea, nausea and vomiting or rash should be managed early and proactively as described in [Section 4.2](#).

Proprietary confidential information.

© 2017 Boehringer Ingelheim International GmbH or one or more of its affiliated companies. All rights reserved.

This document may not - in full or in part - be passed on, reproduced, published or otherwise used without prior written permission.

Table 4.1.4.3:1 Dose reduction scheme for afatinib

AE type and CTCAE Grade	Action	Dose reduction scheme

Events related to study drug:
 
 • Diarrhoea Grade 2 persisting for 7 or more consecutive days despite adequate anti-diarrhoeal medication/hydration • Reduced renal function to \geq Grade 2 as measured by serum creatinine, proteinuria or decrease in glomerular filtration rate of more than 50% from baseline • Any drug related AE Grade \geq3 	
Pause treatment until patient has recovered to Grade \leq1 or baseline¹.
 
Resume treatment at reduced dose according to schedule opposite.
 
If patient has not recovered to Grade \leq1 or baseline¹ within 14 days, study treatment must be permanently discontinued².
	
If patient was treated at dose level 3, resume treatment at dose level 2
 
If patient was treated at dose level 2, resume treatment at dose level 1
 
If patient was treated at dose level 1, resume treatment at dose level 0
 
If patient was treated at dose level 0, resume treatment at dose level -1
 
If patient was treated at dose level -1, discontinue afatinib.

Acute onset and/or unexplained worsening of pulmonary symptoms (dyspnoea requiring supplementation of oxygen with cough and/or fever)
	
Pause afatinib while clinical assessment to exclude ILD is completed.
	
If ILD is ruled out as a cause of symptoms, grade symptoms and relatedness and report as AEs. If AEs are not related, resume afatinib at current dose.
 
If ILD is confirmed, discontinue afatinib.


Acute onset of symptoms indicative of keratitis
	
Pause afatinib while clinical assessment of keratitis is ongoing.
	
If a diagnosis of ulcerative keratitis is confirmed, treatment with afatinib should be discontinued. Unless the treatment benefit for the patient outweighs the risks of worsening keratitis (blindness) in the opinion of the investigator.

Acute onset of symptoms indicative of cardiac failure and/or CTCAE Grade \geq 2 LVEF decrease and/or \geq20% decrease of LVEF from baseline
	
Pause afatinib while clinical assessment is ongoing and until patient recovers to Grade \leq1 or baseline¹
	
If patient has not recovered despite appropriate treatment to Grade \leq1 or baseline¹ within 14 days, study treatment must be permanently discontinued²

1 Baseline is defined as the CTCAE Grade at the start of treatment

2 In the event that the patient is deriving obvious clinical benefit according to the investigator's judgement, further treatment with afatinib will be decided in agreement between the sponsor and the investigator.

In the event of any unrelated adverse events, the investigator may choose to interrupt the medication for up to 14 days, but no dose reduction should occur once treatment is resumed.

Proprietary confidential information.

© 2017 Boehringer Ingelheim International GmbH or one or more of its affiliated companies. All rights reserved.

This document may not - in full or in part - be passed on, reproduced, published or otherwise used without prior written permission.

If the medication is interrupted for more than 14 days, the decision to continue with afatinib will be made by the BI clinical monitor in agreement with the investigator.

